### **11.2 Monitoring and Recording Adverse Events**

Adverse events will be assessed by the investigator or qualified designee and recorded in the CRFs. The investigator should attempt to establish a diagnosis of the event on the basis of signs, symptoms and/or other clinical information. In such cases, the diagnosis should be documented as the adverse event and/or serious adverse event and not described as the individual signs or symptoms. The following information should be recorded:

- Description of the adverse event using concise medical terminology
- Description as to whether or not the adverse event is serious
- The start date (date of adverse event onset)
- The stop date (date of adverse event resolution or return to baseline)
- The severity (grade) of the adverse event
- A description of the potential relatedness of the adverse event to study drug or a study procedure
- Expectedness of the adverse event based on prior observed and documented adverse events
- The outcome of the adverse event

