### **11.3 Grading of the Severity of an Adverse Event**

AEs will be graded in severity according to the NCI Common Terminology Criteria for Adverse Events (CTCAE) Version 5.0. If a CTCAE criterion does not exist, the investigator should use the grade or adjectives: Grade 1 (mild), Grade 2 (moderate), Grade 3 (severe), Grade 4 (life-threatening), or Grade 5 (fatal) to describe the maximum intensity of the adverse event. For cytokine release syndrome, the CRS Grading Scale provided in **Appendix E** will be used to grade severity.

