## **11.6 Dose-limiting Toxicities to Guide Dose Modification**

Dose-limiting toxicity (DLT) is defined as below and will be used to guide potential dose modification as detailed in **Sections 11.7.4 and 12.2.1**.

DLTs will be assessed for 14 days following the first infusion of the TCR-T cell product. The following events will be considered DLTs if they are attributed as at least possibly related to T cell administration. Grading will be done in accordance with the NCI Common Terminology Criteria for Adverse Events ([CTCAE Version 5.0](#) unless otherwise specified.

- Grade  $\geq$  3 allergic reaction related to the TCR-T cell infusion
- Grade  $\geq$  3 autoimmune reactions
- Any Grade 3 or 4 non-hematologic event that has not resolved to < grade 3 by day 28 post T cell infusion
- Grade  $\geq$  3 neurotoxicity of greater than 7 days duration
- Grade  $\geq$  3 neurotoxicity that does not revert to Grade 1 or baseline within 28 days
- Grade  $\geq$  3 seizures that do not resolve to < grade 3 within 3 days
- Grade  $\geq$  4 CRS (using criteria modified from Lee 2014)
- Grade 3 CRS that does not resolve to < grade 3 within 7 days
- Any other toxicity not meeting the above criteria that is deemed by the PI to represent a DLT

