## APPENDIX E: CRS Grading Criteria (CTCAE v. 5.0)

**Definition:** A disorder characterized by fever, tachypnea, headache, tachycardia, hypotension, rash, and/or hypoxia caused by the release of cytokines.

Grade	Description of Symptoms
1: Mild	Fever with or without constitutional symptoms
2: Moderate	Require and respond to moderate intervention: 

• Oxygen requirement < 40%, or

• Hypotension responsive to fluids,

3: Severe	Require and respond to aggressive intervention: 

• Oxygen requirement <math>\geq</math> 40% O2, or

• Hypotension requiring a single vasopressor

4: Life-threatening	Life-threatening; urgent intervention indicated
5: Fatal	Death

a Organ toxicity excludes neurotoxicity, which will be evaluated separately

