## APPENDIX F: Recommended Management of CRS

**ASTCT CRS Consensus Grading**

CRS Parameter	Grade 1	Grade 2	Grade 3	Grade 4
Fever*	Temperature $\geq 38^{\circ}\text{C}$	Temperature $\geq 38^{\circ}\text{C}$	Temperature $\geq 38^{\circ}\text{C}$	Temperature $\geq 38^{\circ}\text{C}$
With				
Hypotension	None	Not requiring vasopressors	Requiring a vasopressor with or without vasopressin	Requiring multiple vasopressors (excluding vasopressin)
And/or: †				
Hypoxia	None	Requiring low-flow nasal cannula ‡ or blow-by	Requiring high-flow nasal cannula ‡ , facemask, nonrebreather mask, or Venturi mask	Requiring positive pressure (e.g., CPAP, BiPAP, intubation and mechanical ventilation)

Organ toxicities associated with CRS may be graded according to CTCAE v5.0 but they do not influence CRS grading.

\*Fever is defined as temperature  $\geq 38^{\circ}\text{C}$  not attributable to any other cause. In patients who have CRS then receive antipyretic or anticytokine therapy such as tocilizumab or steroids, fever is no longer required to grade subsequent CRS severity. In this case, CRS grading is driven by hypotension and/or hypoxia.

†CRS grade is determined by the more severe event: hypotension or hypoxia not attributable to any other cause. For example, a patient with temperature of  $39.5^{\circ}\text{C}$ , hypotension requiring 1 vasopressor, and hypoxia requiring low-flow nasal cannula is classified as grade 3 CRS.

‡Low-flow nasal cannula is defined as oxygen delivered at  $\leq 6\text{L}/\text{minute}$ . Low flow also includes blow-by oxygen delivery, sometimes used in pediatrics. High-flow nasal cannula is defined as oxygen delivered at  $> 6\text{L}/\text{minute}$ .

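### Recording only the CRS diagnosis (11.2) can keep a grade 3 or higher, non-life-threatening organ toxicity out of the dose-decision counts

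*Combined protocol and SAP*

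**What the plan says.** **Recording.** Section 11.2 asks the investigator to seek a diagnosis behind the findings and then says that "the diagnosis should be documented as the adverse event and/or serious adverse event and not described as the individual signs or symptoms". Section 11.1 includes abnormal laboratory findings among the signs that can be adverse events.

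**CRS grade.** Section 11.3 names the scale: "For cytokine release syndrome, the CRS Grading Scale provided in" Appendix E. In that appendix, grades 1 to 3 rest on fever, oxygen requirement and hypotension. Grade 4 is the general entry "Life-threatening; urgent intervention indicated". A footnote reads "Organ toxicity excludes neurotoxicity, which will be evaluated separately", but no visible entry in the table refers to organ toxicity. Appendix F, on CRS management, carries a second scale and states: "Organ toxicities associated with CRS may be graded according to CTCAE v5.0 but they do not influence CRS grading". Section 11.6 points to a third source, criteria modified from a 2014 publication on CRS.

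**What is counted.** Section 11.6 lists as a DLT, if at least possibly related, "Any Grade 3 or 4 non-hematologic event that has not resolved to < grade 3 by day 28 post T cell infusion". It also lists CRS of grade 4 or higher, grade 3 CRS lasting beyond 7 days, and "Any other toxicity not meeting the above criteria that is deemed by the PI to represent a DLT". The dose level 1 steps in 12.2.1 count treatment-related and unexpected toxicity of grade 3 or higher.

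**How events reach the decision.** Under 11.7.4, the clinical operations team abstracts adverse events and presents them to the PI for attribution. The DAC reviews the data after day 28 of each set of 3 or 4 patients.

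**The concern.** The recording rule and the counting rules use different units. Section 11.2 reduces a syndrome to one entry with one grade. Sections 11.6 and 12.2.1 count individual toxicities by their own grade. That is harmless if the grade of the syndrome reflects its worst component. For CRS, as the appendices read, it does not do so below the life-threatening level.

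A hepatic or renal abnormality of grade 3 that is judged part of CRS can therefore sit under an entry of CRS grade 1 or 2. No sentence requires it to be recorded as an event of its own. The cohorts are of 3 to 6 patients, so one uncounted event can change an escalation decision. The same classification feeds the rule in 12.2.1 that ends study treatment for an individual patient. Any loss lowers the counted rate, which favours escalating or continuing.

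**Working it through.** **1. One patient, two readings.** Take a patient with fever, no hypotension and no oxygen need. A grade 3 creatinine or transaminase rise starts within the 14-day DLT window, is judged part of CRS and possibly related to the cells, and is still grade 3 at day 28.

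| | 11.2 followed to the letter | Organ toxicity also recorded |
|---|---|---|
| CRF entries | CRS grade 1 | CRS grade 1, plus a grade 3 organ event |
| 11.6 non-hematologic criterion | Nothing of grade 3 is recorded | Met |
| 12.2.1 dose level 1 count | Nothing of grade 3 is recorded | Counted if unexpected |

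The facts are the same and the count differs.

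**2. Which events are exposed.** A life-threatening organ toxicity can be grade 4 CRS under Appendix E and so a DLT. An event below grade 3 by day 28 does not meet the non-hematologic criterion even when recorded separately. An expected event does not enter the 12.2.1 count. What remains is (a) a non-life-threatening event still at grade 3 or higher on day 28, for 11.6, and (b) a non-life-threatening, related and unexpected event of grade 3 or higher, for 12.2.1.

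**3. The plan's own figures.** The suspension boundaries in 12.2.1 are 2/2, 3/3-4, 4/5-6, 5/7-8, 6/9-10, 7/11-12, 8/13-14 and 9/15. Let f(n,k) be the probability of k toxicities in n patients with no boundary yet crossed:

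f(n,k) = f(n-1,k)(1-p) + f(n-1,k-1)p.

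After each patient from n = 2 to 15, the probability at or above the boundary is moved to suspension. The result is 0.062 at p = 0.20 (stated: about 0.06) and 0.824 at p = 0.60 (stated: about 0.84, a difference of 0.016). The stated figures are reproduced to within two percentage points. They presume that every toxicity is counted.

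**4. Illustration of the effect.** Inputs: true rate p of countable events; assumed share m of those events lost to recording. The counted rate is p(1-m). The documents give no value for m, so a range is shown. I use p = 0.35 because 12.2.1 names 35% as the highest acceptable DLT rate, and p = 0.60 because 12.2.1 quotes it for suspension.

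Dose level 1 escalates on 0 of 3, or on 1 of 3 followed by 0 of 3. With counted rate r and q = 1 - r:

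P(escalate) = q³ + 3r·q²·q³ = q³ + 3r·q⁵.

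- m = 0: r = 0.35, so 0.65³ + 3(0.35)(0.65⁵) = 0.2746 + 0.1218 = 0.396
- m = 10%: r = 0.315, so 0.3214 + 0.1425 = 0.464
- m = 25%: r = 0.2625, so 0.4011 + 0.1718 = 0.573
- m = 50%: r = 0.175, so 0.5615 + 0.2007 = 0.762

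The recursion in step 3 with the counted rate gives:

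| Share lost, m | P(suspend), true rate 35% | P(suspend), true rate 60% |
|---|---|---|
| 0 | 0.261 | 0.824 |
| 10% | 0.199 | 0.701 |
| 25% | 0.124 | 0.484 |
| 50% | 0.045 | 0.175 |

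**The case against.** The best defence is that the counts do not depend on CRF terms. Section 11.6, read literally, counts any persisting grade 3 or 4 non-hematologic event, whatever it is filed under, and the PI may declare any other toxicity a DLT. Section 11.5 records adverse events of all grades. Section 13.2 has CRFs hold all grade 3 to 5 events and the DSMB review all toxicities of grade 3 or higher. Section 11.2 bars only signs and symptoms, and a hepatic or renal injury may be a diagnosis in its own right. Appendix F allows separate grading and so treats organ toxicity as separable from CRS. An unusually severe CRS can itself be unexpected under 11.1.

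Much of this stands. A reader might infer that every grade 3 or 4 organ toxicity within CRS leaves the counts, or that the patient in step 1 meets no DLT criterion. The documents support neither. What they show is 11.2 and 11.6 pulling apart, with nothing saying which governs. Sections 11.5 and 13.2 do not settle it, because 11.2 decides what becomes an entry. Appendix F gives permission, not a requirement. The PI's discretion works only if the event is noticed. An entry of CRS grade 1 gives no cue to judge it unexpectedly severe.

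A second objection concerns Appendix E. Its organ-toxicity footnote has no visible anchor, and the grade 2 list ends in a comma. A line may have been lost or deleted. If the scale does carry organ severity, most of the mechanism falls away, but Appendix E then contradicts Appendix F.

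Neurotoxicity is not part of this point: Appendix E sets it apart, and 11.6 has its own criteria for it.

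**Conclusion.** The point holds as a gap in the recording rules. Under 11.2, a grade 3 or higher organ toxicity that occurs with CRS and is not life-threatening can be recorded as low-grade CRS and be missed in the material abstracted for the DAC. It affects the two groups in step 2 and can move decisions only toward escalating or continuing.

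The size cannot be estimated from the documents. The escalation range of 0.46 to 0.76, against 0.40 with full counting, is an illustration at a true rate of 35%. It assumes that the lost event is the patient's only countable one, that the PI's catch-all is not used, and that the rules are applied mechanically, although 11.7.4 and Appendix H allow overrides.

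A reader might also infer that the stated suspension probabilities are wrong or that a downward bias has been shown. Neither follows: the probabilities reproduce closely, and whether events would be lost depends on how sites read 11.2. The conclusion rests on Appendix E as it can be read now.

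**What to change.** - **Section 11.2:** add that each organ toxicity of grade 3 or higher occurring with CRS is also recorded as its own adverse event, graded by CTCAE v5.0, linked to the CRS episode, and assessed against 11.6 and 12.2.1.
- **Appendix F:** replace the permissive *may be graded* with *will be graded and recorded*.
- **CRS scale:** reconcile 11.3 with Appendix E (including its unanchored footnote), 11.6 and Appendix F, so that one scale is identified for the DLT assessment. Which scale that should be is for the sponsor to decide.

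The CRS grade and the DLT definitions need no change for this purpose. The cost is a protocol wording change and a few extra CRF lines for patients with CRS. The observed toxicity rate may come out slightly higher.

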### **11.3 Grading of the Severity of an Adverse Event**

AEs will be graded in severity according to the NCI Common Terminology Criteria for Adverse Events (CTCAE) Version 5.0. If a CTCAE criterion does not exist, the investigator should use the grade or adjectives: Grade 1 (mild), Grade 2 (moderate), Grade 3 (severe), Grade 4 (life-threatening), or Grade 5 (fatal) to describe the maximum intensity of the adverse event. For cytokine release syndrome, the CRS Grading Scale provided in **Appendix E** will be used to grade severity.

### **11.4 Attribution of Adverse Event**

Association or relatedness to the study agent will be assessed by the investigator as follows:

Definite (must have all 4)	

• Has a reasonable temporal relationship to the intervention

• Could not have readily been produced by the subject's clinical state or have been due to environmental or other interventions

• Follows a known pattern of response to intervention

• Disappears or decreases with reduction in dose or cessation of intervention and recurs with re-exposure

Probable (must have 3)	

• Has a reasonable temporal relationship to the intervention

• Could not have readily been produced by the subject's clinical state or have been due to environmental or other interventions

• Follows a known pattern of response to intervention

• Disappears or decreases with reduction in dose or cessation of intervention

Possible (must have 2)	

• Has a reasonable temporal relationship to the intervention

• Could not have readily been produced by the subject's clinical state

• Could not readily have been due to environmental or other interventions

• Follows a known pattern of response to intervention

Unlikely (must have 2)	

• Does not have a temporal relationship to the intervention

• Could readily have been produced by the subject's clinical state

• Could have been due to environmental or other interventions

• Does not follow a known pattern of response to intervention

• Does not reappear or worsen with reintroduction of intervention

For general AE assessment, an AE is considered related if it is assessed as definitely, probably, or possibly related; unrelated if it is assessed as unlikely related or unrelated.

For determination of IND safety reporting, AE attribution will be assessed according to the suspected adverse reaction definition described in 21 CFR 312.32 as an AE for which there is a reasonable possibility that the drug caused the adverse event where “reasonable possibility” means there is evidence to suggest a causal relationship between the drug and the AE. The IND Sponsor will report suspected adverse reactions that are both serious and unexpected to the FDA as an IND safety report, in accordance with regulations under 21 CFR 312.32.

### **11.5 Adverse Event Reporting Period**

All adverse events (grades 1-5) will be monitored and recorded in study-specific case report forms (CRFs) throughout the investigative phases of the study: from each T cell infusion through day 14 (for purposes of potential dose modification) and in conjunction with standard follow-up time points during the first year following T cell infusion. The detailed collection of AEs will stop at the time of commencement of new anti-tumor therapy.

AEs with an onset date prior to apheresis will not be recorded, except in the case of clinically significant worsening of the AE during the specified monitoring time frame. A subject withdrawn from the study because of an adverse event must be followed until the clinical outcome from the adverse event is determined.

The following events are *not* identified as AEs in this study:

- Disease progression or relapse.
- Hospitalization to facilitate infusions is not considered an AE. Any AE requiring prolongation of this hospitalization will be recorded and patient to applicable SAE reporting.
- Hospitalization to facilitate monitoring/due to the absence of caregiver/any other reason that is not related to T cells. Medical or surgical procedures in and of themselves, including those that

require hospitalization (e.g., surgery, endoscopy, biopsy procedures) are not considered AEs. However, an event or condition requiring such procedures may be an AE.

- Hospitalization that is otherwise unrelated to adverse events.

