## **10.8 Participant discontinuation of active treatment**

A patient will no longer be able to receive active treatment on study (T cells, atezolizumab) for any of the reasons listed below. In this scenario (unless withdrawal of consent or death), a participant will no longer be required to comply with protocol-dictated testing, AE collection, and other timepoints for any of the reasons listed below, with the exception that an attempt will be made to collect samples for RCL and persistence at protocol-dictated timepoints. In this scenario (unless withdrawal of consent or death), the participant will transition to the long term follow up (LTFU) phase of study:

- Progressive disease or development of new metastasis requiring urgent change in treatment following second T cell infusion. Patients can be considered for chemotherapy/radiation for progression between the 1st and second infusions and remain on study if considered appropriate by the PI. Washout between therapies received at time of progression and second lymphodepletion should be either 2 weeks post-radiation or the equivalent of one treatment cycle.
- The participant withdraws consent
- Patient death
- Occurrence of pregnancy
- Participation in another therapeutic trial during the treatment duration of this trial
- Occurrence of an exclusion criterion, which is clinically relevant and affects the subject's safety, if discontinuation is considered necessary by the Investigator or Sponsor
- A patient will no longer be eligible to receive additional therapy if the PI or designee determines that additional T cell infusions are not in the best interest of the patient
- Occurrence of any non-pre-existing grade 3 or higher AEs / repetitive Grade 2 AEDRs that are deemed related to the treatment, except for the exceptions detailed in section 12.

- Cytokine release syndrome requiring pressors for >24 hours or tocilizumab

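### The section 11.5 stop on detailed AE collection conflicts with section 10.8, which keeps patients on study for a second infusion after chemotherapy or radiation

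*Combined protocol and SAP*

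**What the plan says.** Section 11.5 sets the AE collection period. All grades are recorded "from each T cell infusion through day 14 (for purposes of potential dose modification"), and then at standard follow-up points in the first year. The next sentence limits this: "The detailed collection of AEs will stop at the time of commencement of new anti-tumor therapy". Nothing in the section says whether any anti-tumor therapy is exempt, or whether collection can reopen.

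Section 10.8 describes a pathway that meets this limit. Patients who progress between the first "and second infusions and remain on study if considered appropriate by the PI" may have chemotherapy or radiation. A second round of study treatment is still expected, because a gap is specified: "Washout between therapies received at time of progression and second lymphodepletion should be either 2 weeks post-radiation or the equivalent of one treatment cycle".

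Section 10.8 also says who is released from AE collection. On discontinuing active treatment, "a participant will no longer be required to comply with protocol-dictated testing, AE collection, and other timepoints for any of the reasons listed below". The progression entry in that list covers only progression "requiring urgent change in treatment following second T cell infusion".

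Appendix A marks AEs at the lymphodepletion visit, on the infusion day and in every later column. Section 10.6 schedules examinations and laboratory tests after each infusion.

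**The concern.** The patient at issue progresses after the first infusion, has chemotherapy or radiation under 10.8, and then has a second lymphodepletion and infusion. This patient has not discontinued and is still on active study treatment. On the plain words of 11.5, detailed AE collection ended when the intervening therapy began. On the plain words of the preceding sentence, the second infusion opens its own collection window. Site staff could defend either course, and different staff could choose differently.

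The data at stake are used in the plan's own rules:

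- Section 10.8 ends active treatment for repeated grade 2 related events, which requires grade 2 capture.
- Section 12.2.1 withdraws a patient from study therapy for unexpected related toxicity of grade 3 or higher, whenever it occurs.
- The excessive-toxicity proportion in 12.2.1 is not restricted to the first infusion.
- Appendix H lets the Dose Assessment Committee (DAC) depart from the algorithm when minor toxicities accumulate at a dose.

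The target is 15-18 patients in total, so few will be re-treated, and incomplete AE detail on one or two of them would weaken the description of re-treatment safety.

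**Working it through.** The point contains no figure to reproduce, so the check follows one patient through the text.

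1. **First infusion.** Collection opens under 11.5. The 11.6 DLT assessment runs for 14 days after this infusion only. There is no conflict.

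2. **Progression; chemotherapy or radiation starts.** The 11.5 stop is triggered: treatment started for progression is, on ordinary reading, new anti-tumor therapy. Section 10.8 does not release this patient, because its progression entry applies only after the second infusion and the patient otherwise remains on study. The two sections now disagree.

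3. **Second lymphodepletion.** Appendix A marks AEs at the lymphodepletion visit. Under 11.5 the stop is in force, and the per-infusion window has not yet opened because it starts at infusion. So even if each infusion restarts collection, 11.5 leaves this interval uncovered while Appendix A includes it.

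4. **Second infusion and the following days.** The per-infusion sentence requires all grades through day 14 and then at first-year time points. The stop sentence, which follows it and reads as a limit on it, says detailed collection has ended. Neither is given precedence.

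5. **Which events have another route?**
   - Serious events: 11.7.2 requires notice to the sponsor within 24 hours if fatal or life-threatening, and within 2 business days for all SAEs. It states no cut-off at new therapy.
   - Grade 3-5 events: 13.2 says the CRFs will hold their nature and severity, and that the DSMB reviews toxicities of grade 3 or greater together with SAEs. It states no cut-off either.
   - Non-serious grade 1-2 events: 11.7.2 refers non-serious events to CRF completion guidelines, and the only collection period stated for them is the one in 11.5. These are the most exposed.

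6. **Which decisions are touched?** DLT-based dose decisions are largely unaffected because of step 1. The exposed uses are the repeated grade 2 rule, the DAC's review of minor toxicities and the overall safety summary. The grade 3 rule and the excessive-toxicity proportion are exposed less, because step 5 gives grade 3-5 events another stated route.

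7. **Size.** The share affected is the number of re-treated patients who had intervening therapy divided by the number re-treated. The documents give neither count and no second-infusion toxicity rate, so no estimate can be made.

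**The case against.** The strongest reply is that the intent is already clear. Collection is tied to each infusion. Section 10.8 releases patients only for listed reasons, and treatment for progression between infusions is not among them. Section 10.6 sets evaluations after each infusion, and Appendix A marks AEs throughout. Bridging therapy before the first lymphodepletion is mentioned in section 10.4, and nobody would take it to end AE collection. On this view, new anti-tumor therapy means treatment that replaces study treatment, not treatment the protocol permits ahead of a planned infusion.

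Much of this stands as evidence of intent. It does not remove the contradiction: the stop sentence is unqualified, the text available here contains no definition that exempts therapy given under 10.8, and nothing says which sentence governs. That text begins partway through section 10, so an earlier section could contain such a definition; if it does, a cross-reference in 11.5 would be enough.

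A reader might infer something stronger: that all second-infusion toxicity in these patients goes uncollected, that the DAC and DSMB would therefore not see it, and that re-treatment would look safer than it is. The documents do not support this. Only detailed collection stops, the per-infusion sentence points the other way, and serious and grade 3-5 events have the routes in 11.7.2 and 13.2. The direction of any bias would depend on second-infusion toxicity in patients with and without intervening therapy, which the documents do not report.

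**Conclusion.** The conflict is real and unresolved in the text available. Applied literally, 11.5 ends detailed AE collection in a patient whom 10.8 keeps on study for a second lymphodepletion and infusion. The plausible loss is AE detail around that second course, mainly non-serious and lower-grade events, and the second lymphodepletion interval is uncovered by 11.5 even on the more generous reading. First-infusion DLT decisions are largely untouched. The number of patients affected and the direction of any bias cannot be determined.

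The conclusion assumes that chemotherapy or radiation for progression counts as new anti-tumor therapy under 11.5, and that no section outside the available text says otherwise. It takes no position on whether such therapy should be given between infusions or on the washout. The correction is worthwhile because it is cheap and because lower-grade events not recorded at the time may be hard to recover later.

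**What to change.** Reconcile 11.5 with 10.8. State in 11.5 that the stop at new anti-tumor therapy applies only to patients who will receive no further study infusion. For patients kept on study under 10.8, state that AE collection continues, or resumes no later than the start of the second lymphodepletion (or the infusion, if there is none), on the same schedule as after the first infusion. Add a CRF flag for AEs with onset during the intervening therapy so that they can be reported separately.

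The cost is a short amendment to 11.5 and one CRF field. No visits are added, since 10.6 already schedules assessments after each infusion. The small downside is that some recorded events will be due to the intervening therapy; the attribution step in 11.4 and the flag deal with that.
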